12. ADMINISTRATIVE MATTERS

12.1. Disclosure of PMS

The information of this PMS will be posted on ClinicalTrial.gov.

12.2. Quality Control

In accordance with applicable regulations, GCP, and GSK procedures, GSK monitors will contact the site prior to the start of the PMS to review with the site staff the protocol, PMS requirements, and their responsibilities to satisfy regulatory, ethical, and GSK requirements. When reviewing data collection procedures, the discussion will include identification, agreement and documentation of data items for which the CRF will serve as the source document.

GSK will monitor the study to ensure that the:

- Data are authentic, accurate, and complete.
- Safety and rights of subjects are being protected.
- Study is conducted in accordance with the currently approved protocol and any other study agreements, GCP, and all applicable regulatory requirements.

The investigator and the head of the medical institution (where applicable) agree to allow the monitor direct access to all relevant documents.

To ensure compliance with GCP and all applicable regulatory requirements, GSK may conduct a quality assurance audit of the site records, and the regulatory agencies may conduct a regulatory inspection at any time during or after completion of the study. In the event of an audit or inspection, the investigator (and institution) must agree to grant the auditor(s) and inspector(s) direct access to all relevant documents and to allocate their time and the time of their staff to discuss any findings/relevant issues.

12.4. Study and Site Closure

Upon completion or termination of the PMS, the GSK monitor will conduct site closure activities with the investigator or site staff (as appropriate), in accordance with applicable regulations, GCP, and GSK Standard Operating Procedures.

GSK reserves the right to temporarily suspend or terminate the PMS at any time for reasons including (but not limited to) safety issues, ethical issues, or severe non-compliance. If GSK determines that such action is required, GSK will discuss the reasons for taking such action with the investigator or head of the medical institution (where applicable). When feasible, GSK will provide advance notice to the investigator or head of the medical institution of the impending action.

If a PMS is suspended or terminated for **safety reasons**, GSK will promptly inform all investigators, heads of the medical institutions (where applicable), and/or institutions conducting the PMS. GSK will also promptly inform the relevant regulatory authorities of the suspension/termination along with the reasons for such action. Where required by applicable regulations, the investigator or head of the medical institution must inform the IRB/IEC promptly and provide the reason(s) for the suspension/termination.

12.5. Records Retention

Following closure of the PMS, the investigator or head of the medical institution (where applicable) must maintain all site PMS records (except for those required by local regulations to be maintained elsewhere) in a safe and secure location. The records must be easily accessible when needed (e.g., for a GSK audit or regulatory inspection) and must be available for review in conjunction with assessment of the facility, supporting systems, and relevant site staff.

Where permitted by local laws/regulations or institutional policy, some or all of the records may be maintained in a format other than hard copy (e.g., microfiche, scanned, electronic); however, caution must be exercised before such action is taken. The investigator must ensure that all reproductions are legible and are a true and accurate copy of the original. In addition, they must meet accessibility and retrieval standards, including regeneration of a hard copy, if required. The investigator must also ensure that an acceptable back-up of the reproductions exists and that there is an acceptable quality control procedure in place for creating the reproductions.

GSK will inform the investigator of the time period for retaining the site records in order to comply with all applicable regulatory requirements. The minimum retention time will meet the strictest standard applicable to a particular site, as dictated by local laws/regulations, GSK standard operating procedures, and/or institutional requirements.

The investigator must notify GSK of any changes in the archival arrangements, including, but not limited to archival of records at an off-site facility or transfer of ownership of the records in the event that the investigator is no longer associated with the site.

12.6. Provision of Study Results and Information to Investigators

After the PMS completed and analyzed, where required by applicable regulatory requirements, an investigator signatory will be identified for the approval of the clinical study report. The investigator will be provided reasonable access to statistical tables, figures, and relevant reports and will have the opportunity to review the complete study results at a GSK site or other mutually-agreeable location.

If this surveillance evaluate effectiveness of drug GSK will ensure public disclosure of the clinical trial research results via the GSK Clinical Trials Register according to the GSK SOP and provide the investigator with the full summary of the PMS results. In addition, the manuscript would be submitted within 18 months upon completion of data analysis. The investigator is encouraged to share the summary results with the study subjects, as appropriate.

12.7. Personal Information and Data Protection

Records of personally identifiable information will be not included in the study results and managed by a serial number so they will not be included on publication and disclosure of study results. Investigators take responsibility for protecting from personal and medical information leaking.

13. STUDY PUBLICATION

13.1. Ownership

All data generated during this PMS and provided to GSK are the property of GSK.

13.2. Confidentiality

The investigators and other study personnel will keep any information provided by GSK confidential. The information includes this protocol, all data and records generated in the course of conducting this PMS. The investigators and other study personnel will not use the information, data, or records for any purpose other than conducting the PMS. These restrictions do not apply to:

- Information that becomes publicly available through no fault of the investigator of site personnel;
- Information that is necessary to disclose in confidence to an IEC or IRB solely for the evaluation of the study;
- Information that is necessary to disclose in order to provide appropriate medical care to a patient; or
- Study results that may be published, as described in the next paragraph.

13.3. Publication

For any multi-centre study, data from any individual centre must not be published or presented until the complete multi-centre study has been published or presented in full. Any subsequent publications should refer to the published multi-centre findings.

Prior to submitting for publication, presenting, using for instructional purposes or otherwise disclosing the results of the study, the investigator shall allow GSK a period of at least thirty (30) days [or, for abstracts, at least five (5) working days] to review the proposed publication or disclosure prior to its submission for publication or other disclosure. Publications or

disclosures of PMS results shall not include other confidential information of GSK's. If the proposed publication/disclosure risks GSK's patent any invention related to the PMS, the publication or disclosure will be modified or delayed a sufficient time to allow GSK to seek patient protection of the invention. This statement does not give GSK any editorial rights over the content of a publication or disclosure, other than to restrict the disclosure of GSK's confidential information.

Appendix 2. Response Evaluation Criteria In Solid Tumors (RECIST) criteria 1.1

RECIST1.1.pdf

Appendix 3: Supportive Care Guidelines for Diarrhea, Nausea, and Vomiting

These general guidelines are provided to facilitate subject care in the event of diarrhea, thereby avoiding serious complications. Guidelines such as these should never replace sound clinical judgment. Experience thus far suggests that use of monotherapy pazopanib is associated with an increased incidence of diarrhea, primarily of Grade 1 or 2. In rare cases, diarrhea can be debilitating and potentially life threatening, with dehydration, renal insufficiency, and electrolyte imbalances.

Standardized and universal guidelines have been developed by an American Society of Clinical Oncology panel for treating chemotherapy-induced diarrhea [Benson, 2004].

Early identification and intervention is critical for the optimal management of diarrhea.

A subject's baseline bowel patterns should be established so that changes in patterns while on treatment can be identified. An assessment of frequency, consistency, and duration of diarrhea, as well as knowledge of other symptoms such as fever, cramping, abdominal pain, nausea, vomiting, dizziness and thirst should be taken at baseline, permitting identification of patients at high risk of diarrhea. Patients should be educated on signs and symptoms of diarrhea with instructions to report any changes in bowel patterns to the study site physician.

The NCI CTCAE Version 4.0 criteria for defining diarrhea are provided below.

Toxicity Grade	Diarrhea (includes diarrhea of small bowel or colonic origin and/or ostomy diarrhea)
1	Increase of <4 stools/day over baseline; mild increase in ostomy output compared to baseline
2	Increase of 4-6 stools/day over baseline; moderate increase in ostomy output compared to baseline
3	Increase of ≥ 7 stools/day over baseline; incontinence; hospitalization indicated; severe increase in ostomy output compared to baseline; limiting self care activities of daily living
4	Life threatening consequences, urgent intervention indicated
5	Death

Uncomplicated diarrhea is considered mild to moderate and is defined as CTCAE Grade 1 to 2 with no complicating signs or symptoms.

Complicated diarrhea is severe and defined as CTCAE Grade 3 or 4 or Grade 1 or 2 with one or more of the following signs or symptoms: severe cramping, \geq Grade 2 nausea/vomiting, decreased performance status, fever, sepsis, Grade 3 or 4 neutropenia, obvious bleeding, dehydration.

Management Guidelines

Uncomplicated diarrhea of CTCAE Grade 1 or 2:

- Hydration: have subject drink 8 to 10 large glasses (approximately 2 liters) of clear non-caffeinated liquids a day (e.g., broth or electrolyte-containing sports drinks).
- If Grade 2 diarrhea, consider dose reduction of investigational products.
- Dietary modifications: have subject stop all lactose-containing products and eat frequent, small meals
- Pharmacologic intervention using loperamide:
 - Begin loperamide at initial dose of 4 mg followed by 2 mg every 4 hours or after every unformed stool. The recommended maximum daily dose of loperamide is 16 mg/day.

- Continuation of loperamide is suggested until diarrhea-free for 12 hours.
- If mild to moderate diarrhea persists for more than 24 hours, administer loperamide 2 mg every 2 hours and pursue evaluation for other treatable causes.
- If mild to moderate diarrhea persists after 48 hours total treatment with loperamide, discontinue study drug(s) and consider initiation of second-line agents (lomotil, octreotide).

Complicated diarrhea of CTCAE Grade 3 or 4 diarrhea or Grade 1 or 2 with complicating features requires aggressive management:

- Subject must call study site physician immediately in response to any event of severe diarrhea with or without complications as listed above.
 - Hospitalization may be required for subjects most at risk for life-threatening complications.
- Interrupt investigational products until symptoms resolve; consider reintroducing at a reduced dose (discuss with GSK Medical Monitor or designee).
- If loperamide has not been initiated, begin loperamide usage immediately at an initial dose of 4 mg followed by 2 mg every 2 hours or after every unformed stool. The recommended maximum daily dose of loperamide is 16 mg/day.
- If no improvement in severity after 24-hours of maximal loperamide dosing, subject must visit study site and be evaluated:
 - For dehydration, use intravenous fluids as appropriate.
- Antibiotic therapy should be considered in patients, who present with signs and symptoms of bacterial diarrhea such as fever, bloody diarrhea, and presence of fecal leukocytes. Investigators should have a low threshold to start such treatment in patients with Grade 3 or Grade 4 neutropenia.
- Before initiation of antimicrobial therapy, stool cultures should be obtained. When bacterial etiology for diarrhea is suspected, study-treatment and anti-motility agents (loperamide or others) should be held.
- Intervention should be continued until diarrhea free for 24 hours.

Alternative Pharmacologic Intervention for Uncomplicated and Complicated Diarrhea

- Lomotil (diphenoxylate 2.5 mg + atropine 0.025 mg) can be used. The recommended dose is 2 tablets 4 times daily. When diarrhea is under control, a dose reduction should be attempted.
- The synthetic octapeptide, octreotide, has been shown to be effective in the control of diarrhea induced by fluoropyrimidine-based chemotherapy regimens when administered as an escalating dose by continuous infusion or subcutaneous injection. Octreotide can be administered at doses ranging from 100 µg twice daily to 500 µg 3 times daily, with a maximum-tolerated dose of 2000 µg 3 times daily in a 5-day regimen.

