6.2. Dosage and administration

Votrient will be administered as described on the prescribing information. The treatment of patient does not be affected by this PMS.

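### Appendix 3's two-hourly loperamide schedules cannot be kept for a full day within its own 16 mg/day maximum, and its drug-stopping wording sits badly with the non-interventional design

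*Protocol*

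**What the plan says.** Appendix 3 of the protocol gives supportive-care guidance for diarrhea in two parts.

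**Uncomplicated (Grade 1 or 2).** The starting schedule is "Begin loperamide at initial dose of 4 mg followed by 2 mg every 4 hours or after every unformed stool". The daily limit follows directly: "The recommended maximum daily dose of loperamide is 16 mg/day". A later bullet steps up the dose: "If mild to moderate diarrhea persists for more than 24 hours, administer loperamide 2 mg every 2 hours". That bullet does not mention the limit. The next decision point is "If mild to moderate diarrhea persists after 48 hours total treatment with loperamide, discontinue study drug(s".

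**Complicated (Grade 3 or 4, or lower grades with complicating features).** The instruction, where loperamide has not yet been started, is "begin loperamide usage immediately at an initial dose of 4 mg followed by 2 mg every 2 hours or after every unformed stool". The same 16 mg/day sentence follows in that bullet.

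**The product itself.** For uncomplicated diarrhea that outlasts loperamide treatment, the appendix says "discontinue study drug(s) and consider initiation of second-line agents". For complicated diarrhea it says to interrupt the product and to discuss reintroduction with the sponsor's medical monitor. Where a bacterial cause is suspected, study treatment is to be held.

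Section 3 describes the surveillance as non-interventional. Section 6.2 says "The treatment of patient does not be affected by this PMS". Section 7 leaves concomitant medication to local practice.

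**The concern.** A fixed dose at a fixed interval implies a daily total, and that total can be compared with the daily maximum printed beside it. The four-hourly schedule is compatible with the maximum; the two-hourly schedules are not. A site that follows the step-up bullet as written for a day passes the limit given a few lines earlier. Diarrhea is an event that the appendix itself associates with pazopanib, and the protocol plans for 3000 subjects, so the text may well be used. This is a patient-safety matter before it is a statistical one.

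The second issue concerns the nature of the study. A surveillance that says it leaves treatment alone also tells sites when to stop or interrupt the product, and gives the sponsor a part in restarting it. The primary endpoint is the occurrence of adverse events under routine use, so the protocol should be clear about whether it influences that use.

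**Working it through.** **Inputs, all from Appendix 3**
- Stated maximum: 16 mg/day.
- Starting schedule, uncomplicated: 4 mg, then 2 mg every 4 hours.
- Step-up, uncomplicated: 2 mg every 2 hours, from just after 24 hours until the 48-hour decision point, so about one full day.
- Complicated: 4 mg, then 2 mg every 2 hours.

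**Formula.** Total in 24 hours = loading dose + 2 mg × number of interval doses. A day is taken as 24 consecutive hours with dosing overnight. The alternative of dosing after each unformed stool is not a fixed amount and is not counted.

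**Check on the schedule that should fit.** Four-hourly: 4 + 5 × 2 = 14 mg, or 4 + 6 × 2 = 16 mg if a dose at hour 24 is counted. Both are within 16 mg, so the counting rule does not itself create a conflict.

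**Step-up, uncomplicated**
- Doses at hours 0, 2, …, 22: 12 × 2 = 24 mg; 24 / 16 = 1.5.
- The maximum is reached with the eighth dose (8 × 2 = 16 mg), at hour 14.

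**Complicated, first day**
- 4 + 2k = 16 gives k = 6, so the maximum is reached at hour 12.
- If continued to hour 22: 4 + 11 × 2 = 26 mg; 26 / 16 = 1.63. Counting a dose at hour 24 gives 28 mg; 28 / 16 = 1.75.
- Each later day without a loading dose: 12 × 2 = 24 mg.

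**Could a shorter dosing window rescue the two-hourly interval?** Without a loading dose, a 16-hour window gives 8 × 2 = 16 mg. With it, a 14-hour window gives 4 + 6 × 2 = 16 mg. Windows of about that length would fit, but the appendix states none.

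**Wording on the product, side by side**

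| Appendix 3 | Body of the protocol |
|---|---|
| Discontinue after 48 hours of loperamide without resolution (imperative) | Section 6.2: treatment is not affected by the surveillance |
| Interrupt in complicated diarrhea (imperative); reintroduction discussed with the sponsor's medical monitor | Section 3: non-interventional |
| Hold study treatment if a bacterial cause is suspected | Section 6.2: product given according to the prescribing information |
| Set loperamide schedules | Section 7: concomitant medication follows local practice |
| Reduced dose for Grade 2, or at reintroduction: only to be considered | No direct conflict |

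**The case against.** The strongest reply is that a daily maximum caps any interval schedule. In the complicated bullet this is the natural reading: the limit follows the schedule at once, and a site that reads the whole bullet stops at 16 mg. A reader might infer that the protocol instructs 26 mg on the first day; the bullet does not support that. What stands is that the two-hourly interval cannot be kept beyond about hour 12 and the text does not say what happens then. A later bullet makes a site visit depend on a day of maximal loperamide dosing, without saying whether maximal means the daily limit or the full two-hourly schedule.

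For the uncomplicated step-up the reply is weaker. The limit does appear earlier under the same loperamide heading and is worded per day, so it can be read as general. But the step-up is a separate imperative placed after it, raises the dosing rate, and says nothing about the limit. The 24 mg figure does assume uninterrupted overnight dosing for a full day.

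On the product wording, the appendix opens by presenting itself as general guidance that does not displace clinical judgment. In the text available, the body sections refer to Appendices 1 and 2, but none requires sites to follow Appendix 3. Both facts soften the conflict with Section 6.2. They do not remove it, because stopping and interruption are still written as instructions and the sponsor's monitor is still given a role. A reader might also infer that dose reduction is directed; it is only to be considered.

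**Conclusion.** The concern holds in two parts of unequal weight.

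The main part is an internal contradiction in Appendix 3. The uncomplicated step-up amounts to 24 mg over 24 hours against a stated 16 mg/day, an excess of 8 mg or 50%, assuming round-the-clock dosing. The complicated schedule has the same incompatibility in milder form: its own bullet carries the limit, so the defect is an interval that cannot be sustained for a full day, with no statement of which figure governs. The step-up bullet must be corrected because it bears on patient safety.

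The secondary part is that the wording on interrupting, holding and discontinuing the product, together with the monitor's role, sits badly with Sections 3, 6.2 and 7. It is a matter of consistency, softened by the appendix's advisory introduction, and does not carry the same weight.

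A reader might go further and conclude that the appendix distorts the exposure or the adverse-event frequency and severity that the surveillance reports. That is possible, but the protocol gives no figure from which to size it. The prescribing information is not at hand, so it cannot be said that sites would otherwise have acted differently. No statistical quantity in the protocol changes.

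**What to change.** The sponsor's clinical and safety functions should:

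1. Reconcile both two-hourly loperamide schedules with the stated daily maximum, say explicitly which governs, and carry the result into the step-up bullet and the later reference to maximal dosing.
2. Reconcile the interruption, hold and discontinuation wording, and the medical monitor's role, with Sections 3, 6.2 and 7.
3. Reissue Appendix 3 to sites.

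Which dose, interval or stopping rule is right is for those functions to decide; none is proposed here. The cost is a revision of the appendix and a letter to sites. Sample size, endpoints and analyses are unaffected.

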1.1 Nausea and Vomiting

Every attempt should be made to control nausea and vomiting in subjects who have emesis and are unable to retain pazopanib.

Routine pre-medication for nausea is not necessary, but symptomatic subjects should be treated with standard anti-nausea/anti-emetic therapy as necessary.

If a subject vomits after taking study medication, the subject should be instructed not to take a replacement dose on that same day. The subject should resume taking pazopanib at the next

CONFIDENTIAL
Votrient PMS

Study identifier:115578
GlaxoSmithKline Korea

Protocol Ver.2

scheduled dose on the following day. If vomiting persists, then the subject should contact their physician.

To prevent or treat nausea and vomiting standard medications are recommended. Depending upon approved medications in your region, these may include: 5-HT₃ receptor antagonist (granisetron, ondansetron, dolasetron mesylate); NK-1 receptor antagonists such as aprepitant, metoclopramide, phenothiazines (prochlorperazine); corticosteroids, (dexamethasones, prednisone); and cannabinoids (dronabinol).

Reference:

Study Identifier: 115578
GlaxoSmithKline Korea


1.1 background
	
NA
	
Soft Tissue Sarcoma (STS) is a rare group of heterogeneous mesenchymal cancers originating from connective tissue. The annual incidence of STS is around 2-3/100,000. Overall, STS account for approximately 1% of all malignancies, while they give rise to 2% of the total cancer-related mortality. The 5-year survival in Europe for adult STS (excluding visceral STS) averages 60%, with substantial geographic variations. [Storm et al, 1998] The median survival time in patients with metastatic STS is usually < 12 months.
 
Surgery is usually the first line of management for localized disease. Standard treatment is generally a wide surgical excision or even more radical surgery of the primary tumor combined with adjuvant radiotherapy in selected cases. The addition of post-operative radiotherapy appears to reduce the rate of local recurrence. [Leibel et al, 1982] However, even optimal local treatment does not prevent the occurrence of distant metastases in many patients, especially those with high-grade tumors. Although the effect of adjuvant chemotherapy has been studied by several groups, the results do not allow to draw any final conclusions. An international meta-analysis indicated an effect of adjuvant systemic treatment on progression free survival but did not show a significant effect on overall survival. [Sarcoma Meta-analysis Collaboration, 1997] STS metastasizes primarily to the lungs but also to bone, liver and other organs, depending on the subtype. Chemotherapy is widely used in the treatment of irresectable advanced disease, basically with a palliative intent, as most initially chemotherapy-sensitive patients will ultimately relapse and present at that point with chemotherapy-resistant disease.
 
Clinical efficacy and safety of pazopanib in soft tissue sarcoma patients have been established in a randomized double-blind placebo-controlled Phase III study that enrolled 369 randomized pts (246 pazopanib, 123 placebo). The progression-free survival (PFS) per independent review is significantly prolonged with pazopanib (median: 20 vs 7 weeks; HR=0.31, 95% CI 0.24-0.40, P<0.0001).

---------------------------	-----------	---

STS background information updated

		
The interim analysis for overall survival shows a statistically non-significant improvement of pazopanib vs placebo (median: 11.9 vs 10.4 months, HR=0.83, 95% CI 0.62-1.09). Main on-therapy grade 3-4 toxicities in the pazopanib vs placebo arm respectively: fatigue (13%, 6%), hypertension (7%, nil), anorexia (6%, nil), and diarrhea (5%, 1%). Similarly, thromboembolic events (grade 3-5) (3%, 2%), LVEF drop of > 15% (8%, 3%), [Van et al, 2011]
	
Indication was revised to add STS

3. PMS design overview
	
 • Indication: Advanced renal cell carcinoma • Votrient will be administered for the treatment of advanced renal cell carcinoma as described the prescribing information of Votrient. 	
 • Indication: 
 1. Advanced renal cell carcinoma 2. Advanced soft tissue sarcoma who have received prior chemotherapy • Adipocytic soft tissue sarcoma or gastrointestinal stromal tumors has not been demonstrated. • Subjects treated and/or will be treated with Votrient according to the prescribing information will be enrolled. 	

4.2 Eligibility criteria
	
4.2. Eligibility criteria
 
The investigators enroll advanced renal cell carcinoma patients administered Votrient at the site.
 
All subjects must satisfy the following criteria at PMS entry according to KFSA PMS regulation:
 
4.2.1. Inclusion criteria
 
 • Subjects with indication in the prescribing information • Subject who received Votrient as described the prescribing information 
4.2.2. Exclusion Criteria
 
 • Subjects have contraindication according to the prescribing information 	
4.2. Eligibility criteria
 
The investigators enroll advanced renal cell carcinoma or Soft Tissue Sarcoma (STS) patients administered Votrient at the site.
 
All subjects must satisfy the following criteria at PMS entry according to KFSA PMS regulation:
 
 • Subject who received Votrient as described the prescribing information • Subject who don't have contraindication according to the prescribing information • Subject is willing and able to provide written informed consent 	
To reflect the Prescribing information, Eligible criteria was amended.
 
And the informed consent required due to the revised local regulations.

CONFIDENTIAL
Votrient PMS

Protocol Ver.2

Study identifier: 115578
GlaxoSmithKline Korea

Table 1 Overview of PMS procedures
	
The every-8week assessment of AE and tumor will be recommended. Disease assessment will be done by the study site's institutional standard.
	
The every-4week assessment of AE and tumor will be recommended. Disease assessment will be done by the study site's institutional standard.
	
Clinically, assessment of tumor made every 4-week

9.4 Recording of AEs and SAEs
	
From the time a subject prescribed the medicine until one month after he or she has completed treatment (including any follow-up period), AE/SAE will be reported promptly to GSK
	
From the time a subject agree to his or her participating in this PMS until one month after he or she has completed treatment (including any follow-up period), AE/SAE will be reported promptly to GSK.
	
To reflect the changes regarding informed consent process


10. Reporting of pregnancy
	
Any subject who becomes pregnant should be advised to discontinue Votrient. The investigator will collect pregnancy information on any subject who becomes pregnant while participating in this PMS. The investigators will record pregnancy information on the Pregnancy Report Form and submit it to GSK within 24 hours of learning of a subject's pregnancy. The subject will be instructed to inform pregnancy if investigator get this information this will be forwarded to GSK. While pregnancy itself is not considered an AE or SAE, any pregnancy complication or elective termination will be recorded as an AE or a SAE.
 
Follow the subject to determine the outcome of the pregnancy and forward the outcome information to GSK no later than 6 to 8 weeks following the estimated delivery date.
	
Any subject in person or his or her partner who becomes pregnant should be advised to discontinue Votrient. The investigator will collect pregnancy information on any subject in person or his or her partner who becomes pregnant while participating in this PMS. The investigators will record pregnancy information on the Pregnancy Report Form and submit it to GSK within 24 hours of learning of a subject's pregnancy. The subject will be instructed to investigator of inform pregnancy if investigator get this information this will be forwarded to GSK. While pregnancy itself is not considered an AE or SAE, any pregnancy complication or elective termination of a pregnancy for medical reasons will be recorded as an AE or a SAE.
 
Follow the subject to determine the outcome of the pregnancy and forward the outcome information to GSK no later than 6 to 8 weeks following the estimated delivery date
	
To reflect the changes in the PV code


11. Data analysis and statistical consideration
	
11.1.Primary endpoint
 
 • Occurrence of adverse events after Votrient administration. 
11.2.Secondary endpoints
 
 • Occurrence of unexpected or serious adverse event after Votrient administration • Effectiveness of Votrient by indication • (...) 
11.5.Analysis population
 
Two populations will be considered in the analysis:
 
 - Safety population 
All subjects who receive at least one dose of the drug and at least once safety assessment will be safety population. This is the primary population for the analyses of the safety data.
 
 - Effectiveness population 
All subjects who complete all procedure according to this protocol will be efficacy population. This is the primary population for the analyses for the effectiveness data.
	
11.1.Primary endpoint
 
 • Occurrence of adverse events after Votrient administration by indication 
11.2.Secondary endpoints
 
 • Occurrence of unexpected or serious adverse event after Votrient administration by indication • Effectiveness of Votrient by indication • (...) 
11.5.Analysis population
 
Two populations will be considered in the analysis:
 
 - Safety population 
All subjects who receive at least one dose of the drug and at least once safety assessment will be safety population. This is the primary population for the analyses of the safety data.
 
 - Effectiveness population 
All subjects who complete all procedure according to this protocol will be efficacy population. This is the primary population for the analyses for the effectiveness data.
 
Both analysis will be conducted based on each indications.
	
Major analysis will be performed indication

12.7 Personal Information and Data Protection
	
NA
	
Records of personally identifiable information will be not included in the study results and managed by a serial number so they will not be included on publication and disclosure of study results. Investigators take responsibility for protecting from personal and medical information leaking.
	
To protect the patients privacy

